7.2.1.6 Imaging and Response Evaluation

Imaging studies should include a diagnostic CT scan of the chest, abdomen, and pelvis with PO and IV contrast (unless medically contraindicated). Patients may undergo other modalities such as an MRI instead of a CT scan at the treating physician's discretion if appropriate (such as patient allergy to CT contrast, extremity tumors, bone metastases requiring bone scans, etc).

Response evaluation will occur every 8 weeks (as measured from Cycle 1, Day 1), and at the off study visit (if not performed within the last four weeks). Tumor response and/or disease progression will be assessed by the modality(ies) used prior to treatment. Patients will continue to remain on study as long as there is no evidence of progression of disease and the therapy is adequately tolerated.

7.2.1.7 Adverse Event Evaluation

The Principal Investigator or Sub-investigators will assess adverse events, laboratory data and vital signs throughout the study. Adverse events will be assessed by NCI CTCAE Version 4.0.

http://ctep.cancer.gov/protocolDevelopment/electronic_applications/docs/ctcae4.pdf

The investigators will monitor each subject for clinical and laboratory evidence of adverse events on a routine basis throughout the study. The investigator will assess and record any adverse event in detail including the date of onset, event diagnosis (if known) or sign/symptom, severity, time course, duration and outcome, relationship of the adverse event to study drug, and any action(s) taken. For serious adverse events not considered "probably related" to study drug, the investigator will provide an "Other" cause of the event. For adverse events to be considered intermittent, the events must be of similar nature and severity. Adverse events, whether in response to a query, observed by site personnel, or reported spontaneously by the subject will be recorded. All adverse events will be followed to a satisfactory conclusion.

7.2.1.8 Research Sample Handling Details

All tumor and blood samples will be labeled with the date, protocol number, and protocol assigned patient number.

At baseline (before starting Regorafenib), patients will each be asked to undergo

- peripheral blood draw (7 K2 EDTA lavender top tubes)
- tumor biopsies

Two –three weeks (14-21 days) after starting Regorafenib,

- Peripheral blood draw (7 K2 EDTA lavender top tubes)
- A second tumor biopsies (optional)

7.2.1.9 Peripheral blood samples

Further peripheral blood samples (7 K2 EDTA lavender top tubes) will be collected after initiation of cycle 2, and then at the beginning of every treatment cycle for the duration of regorafenib therapy, up to a total of 8 blood draws.

Specifically, peripheral blood will be collected and banked for miRNA, and mutated DNA analysis.

A peripheral blood sample (7 K2 EDTA lavender top tubes) will also be obtained upon disease progression.

The peripheral blood samples will be sent to Georgetown University Medical Center for storage then distribution to [name] lab and Caris Life Sciences ([name]; Email: [contact]; [contact]) for storage and distribution.

7.2.1.10 Tumor Biopsies

The second tumor biopsy (at 2-3 weeks) can be waived in case of patient refusal, complications after the first biopsy or if the investigator deems the biopsy unsafe.

Tumor samples obtained at Georgetown Hospital and other sites will be collected by the staff of the biospecimen bank. Two specimens will be placed in biopsy cassettes embedded in optimal cutting temperature compound (OCT) and snap frozen within 15 min in dry ice or liquid nitrogen and subsequently stored at -80 until further use. The OCT embedded frozen core needle biopsy samples will be stored in the Georgetown University laboratory then shipped to the laboratory of [name] (George Mason University, [name]; Email: [contact]; [contact]) via FedEx medical shipment service after the last sample has been obtained or two years after the first sample has been obtained whichever occurs first. Once at George Mason University tissue-based laser capture microdissection and protein pathway activation mapping via reverse phase protein array analysis will take place. The rest of the samples will be placed in formalin and then paraffin blocks will be formed to be sent to Caris for CMI testing. Only the baseline tumor samples should be sent to Caris. Please see Appendix 14.1 for specimen requirements.

EVENTS TABLE and STUDY CALENDAR

Baseline evaluations are to be conducted within 28 days prior to start of protocol therapy. Scans and x-rays must be done ≤ 4 weeks prior to the start of therapy. Unless otherwise noted, a standard window of -1 day to + 2 days will be considered acceptable for all testing and evaluations (will not be considered study deviation). In the event that the patient's condition is deteriorating, laboratory evaluations should be repeated within 48 hours prior to initiation of the next dose of therapy.

	Screening Day -28 to -1	C1D1 & C2D1	Day 1 - 21 of every Cycle; starting C1	C1 D 14- 21	C1D14 & C2D14	Day 1 of each cycle starting cycle 2	Every 8 weeks	Disease progression or end of treatment ⁸
Informed consent	X							
Demographics	X							
Medical history	X							
Concurrent meds	X	X			X	X		X
β -HCG ¹	X							
Physical Exam	X	X			X	X		X
Vital signs	X	X			X	X		X
Height	X							
Weight	X	X			X	X		X
Performance status	X	X			X	X		X
Oral Regorafenib		X	X		X	X		
CBC with diff	X	X			X	X		X
Serum chemistries ²	X	X			X	X		X
PT/INR/PTT ⁷	X							
CEA ³	X	X				X		X
Adverse event evaluation	X	X			X	X		X
Radiological evaluation and tumor measurement ⁴	X						X	X ⁵
Research Biopsy	X			X				
Research serum samples ⁶	X			X		X		X

¹ A serum pregnancy test (women of child bearing potential) at screening only. However, the test may be repeated at the discretion of the investigator at any time during the study.

² Serum chemistry will include sodium, potassium, chloride, BUN, bicarbonate creatinine, AST, ALT, total bilirubin, direct bilirubin, albumin, total protein and alkaline phosphatase

³ CEA should be taken on D1 monthly

⁴ Tumor measurements will be obtained by CT scan (or MRI at physician discretion) using RECIST criteria. If patient insurance will not cover a CT/MRI scan within 14 days of regorafenib treatment then a scan within 4 weeks of treatment is acceptable.

⁵ Only if not performed within the last 4 weeks

⁶ Patients will undergo peripheral blood collection for research purposes every 4 weeks for up to 8 blood draws (if still actively on study for that long)

⁷ PT/INR/PTT is only performed at screening unless especially required at 4 weeks by the investigator.

⁸ 30 days after the patient's "end of treatment" visit, a 30-day follow-up patient survival assessment will be made by phone.

8. Endpoints

8.1 Primary endpoint:

8.1.1 Level of serum miRNAs at baseline, 4 and 8 weeks of study treatment

8.2 Secondary endpoints:

8.2.1 Eight-week clinical benefit rate (CBR):

Defined as proportion of patients who achieve completed response (CR) any time + partial response (PR) any time + stable disease (SD) at 8-week and will be measured every eight weeks based on the RECIST criteria version 1.1.

8.2.2 Objective response rate (ORR):

Will follow the RECIST criteria version 1.1 and will be defined as partial response (PR) or complete response (CR). Patients who are lost to follow-up without a valid response assessment will be classified as non-responders.

8.2.3 Progression free survival (PFS):

Defined as the number of days from study entry until progression or death; patients who are alive and free from progression on the date of closing follow-up will be censored on that date.

8.2.4 Overall survival (OS):

Defined as the time in days from study entry until death; patients who are alive on the date of closing follow-up will be censored on that date. All events of death will be included.

8.2.5 Safety:

Assessed by determining the percent of subjects who experience unacceptable (Grade 3/4) adverse events and by describing the safety profiles; adverse events will be summarized by the common terminology criteria for adverse events (CTCAE version 4.0).

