7.2 Study Procedures (details are provided in the events table (Page 42))

7.2.1 Subject assessments

Physical examinations (including neurological assessment), vital signs (vital sign determinations include heart rate, blood pressure and body temperature - *Vital signs should be taken after a 5-minute resting period. Labs will then be drawn once the vital signs are recorded*), performance status, chemistry, hematology, medication review, and adverse event evaluations will be conducted at screening, on C1D1, C1D14, C2D1, C2D14, D1 of every cycle starting C3, and at the off study visit. Study procedures may be performed 2 days before the scheduled visit date, due to unforeseen or unavoidable circumstances.

Body weight will be recorded during every physical exam. The subject will wear lightweight clothing and no shoes during weighing. Height will be measured at the Screening Visit only; the subject will not wear shoes.

30 days after the patient's "end of treatment" visit; a 30-day follow-up patient survival assessment will be made by [contact] Tumor Imaging and Response Evaluation

Baseline imaging (CT scan) will be carried out for all cohorts within 28 days prior to regorafenib therapy—and then must be performed every 8 weeks (as near to Day 1 as possible; every 2 cycles) following initiation of regorafenib treatment.

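### No adverse event evaluation is scheduled after the end-of-treatment visit and the 30-day call covers survival only, so late-onset events may be under-ascertained

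*Combined protocol and SAP*

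**What the plan says.** Section 7.2.1 lists the scheduled evaluations: "adverse event evaluations will be conducted at screening, on C1D1, C1D14, C2D1, C2D14, D1 of every cycle starting C3, and at the off study visit". The events table agrees. Its last column with adverse event evaluation marked is the one for disease progression or end of treatment.

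One contact follows, 30 days after that visit. Footnote 8 of the events table specifies it as "a 30-day follow-up patient survival assessment will be made by phone". Section 7.2.1 has the matching sentence, "a 30-day follow-up patient survival assessment will be made by", whose ending is lost in the text available. Neither place mentions adverse events.

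Other sections keep collection open in part. Section 7.2.1.7 says "All adverse events will be followed to a satisfactory conclusion" and also "Adverse events, whether in response to a query, observed by site personnel, or reported spontaneously by the subject will be recorded". For each event the investigator records, among other items, the "relationship of the adverse event to study drug". Section 8.4.5.1 has SAEs followed until they resolve or stabilize and reported to the manufacturer within 24 hours, with no end date for reporting.

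Safety is a secondary endpoint (Sections 8.2.5 and 9.2.2): the percentage of subjects with Grade 3/4 events. Section 9.3.2 tabulates on-study AEs and SAEs by worst grade and does not say when on-study ends.

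**The concern.** After the end-of-treatment visit no one is told to ask a patient about new adverse events, although a call to that patient is already planned. A new event in those 30 days enters the data only if the patient volunteers it or the site happens to learn of it. That is passive ascertainment, and it is likely to be weakest for non-serious events.

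The analysis adds a second uncertainty. Because on-study has no defined end, a late event that is reported could be counted by one site and left out by another, and this is a multi-site trial.

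Both problems push the safety endpoint the same way. An event that is not sought, or is recorded but excluded, can only lower the percentage with Grade 3/4 events.

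**Working it through.** The plan states no figure that depends on this point, so there is none to reproduce. The check sets the provisions side by side, followed by a calculation for scale.

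**What each provision does after the end-of-treatment visit**

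- *Scheduled evaluations (Section 7.2.1, events table):* none remain.
- *30-day call (footnote 8, Section 7.2.1):* survival status only.
- *Follow-up of adverse events (Section 7.2.1.7):* applies to events already recorded, including any that worsen.
- *Spontaneous reports (Section 7.2.1.7):* recorded if volunteered. The wording also covers answers to a query, but no query is scheduled after the visit.
- *SAE follow-up and reporting (Section 8.4.5.1), events of special interest (Section 8.4.5.3):* no end date, but they apply once the site knows or suspects the event.
- *Medical supervision of removed subjects (Section 5.2.1):* concerns care, not data collection.
- *Routine monitoring (Section 7.2.1.7):* investigators look for "clinical and laboratory evidence of adverse events on a routine basis throughout the study". Section 7.2.1.6 keeps patients on study while they are free of progression and tolerating therapy, and Section 7.2.1 calls the last visit the off-study visit. On that reading routine monitoring ends there, though the documents do not say so outright.
- *Definition of an adverse event (Section 8.4.3):* starts at consent and gives no stop point.

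Known events and volunteered events are covered. New-onset events that nobody volunteers are not.

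**Scale**

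Input: N = 40 (Synopsis and Section 9.4), taken as the number treated. One patient whose only Grade 3/4 event is missed changes the percentage by 1/40 = 0.025, or 2.5 points.

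The documents give no rate for such patients, so a range is assumed. For rate p, the expected number is 40p and the chance of at least one is 1 − (1 − p)^40.

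| Assumed p | Expected patients | Chance of at least one |
|---|---|---|
| 1% | 0.4 | 33% |
| 2.5% | 1 | 64% |
| 5% | 2 | 87% |
| 10% | 4 | 99% |

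If every such event were missed, the expected understatement would equal p itself, that is 1 to 10 points over this range. Any that are volunteered and tabulated reduce it.

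**The case against.** The strongest reply is that the plan does collect adverse events after treatment. Sections 7.2.1.7 and 8.4.5.1 follow known events and SAEs with no cut-off at the last visit, and causality is assessed for every event recorded (Section 8.4.4.3). A patient who stops because of toxicity is therefore followed for that toxicity. This stands. A reader might infer from the schedule that events are simply not collected after the visit and that their relation to drug is lost. The documents do not support that.

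A reader might also infer that a death learned of on the call would come with no adverse event data. Section 8.4.3 makes a fatal event an SAE, and Sections 8.4.4.3 and 8.4.5.1 then require a causality judgment and a report. No exception is made for deaths learned of by phone. What remains true is that the call is not specified to ask for cause of death or preceding events.

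It is also tempting to size the gap by comparing 30 days with the 1.9-month median PFS that Section 1.2.2 cites from the CORRECT trial. That would give a share of calendar time, not of events. It would also take PFS as treatment duration, from a trial dosed at 160 mg when this one starts at 120 mg, and would assume constant risk and no capture after the visit.

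Two further points have weight. Section 8.4.5.1 refers to a pharmacovigilance section of the contract, which is not available here and may set an SAE reporting window. And this is an uncontrolled exploratory study of an approved drug, with safety as a descriptive secondary endpoint, so the stakes are modest. Neither point supplies an active query for new events or a definition of on-study.

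**Conclusion.** The concern holds in limited form. New-onset adverse events in the 30 days after the end-of-treatment visit are not actively sought, and the tabulation window is undefined. Late-onset events may be under-ascertained, and any resulting error in the Grade 3/4 percentage is downward.

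The size cannot be derived from the documents. The 2.5 points per missed patient assumes 40 treated patients and counts only those with no other Grade 3/4 event. The rates in the table are assumptions. The primary miRNA endpoint is not affected. This is an inexpensive improvement worth making, not a flaw that threatens the study.

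**What to change.** - In footnote 8 of the events table and in Section 7.2.1, add to the existing 30-day call a query for new or worsening AEs and SAEs, with relationship to drug, and cause of death where relevant.
- In Section 9.3.2, define on-study to include events up to that call, so that all sites and the safety tables use the same window.

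The cost is a few more questions on a call already scheduled, with the matching data entry, and possibly slightly higher reported event rates. No visit is added, and no dosing or clinical rule changes.

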8.2.6 Activation status of phosphoproteins in tissue specimens

At baseline and 2-3 weeks into treatment; as measured by RPMA assay

8.2.7 Presence mutated DNA in serum at baseline, 4 and 8 weeks of study treatment

8.3 Definitions

Response and progression will be evaluated in this study using the new international criteria proposed by the Response Evaluation Criteria in Solid Tumors (RECIST) version 1.1 Committee. Changes in only the largest diameter (unidimensional measurement) of the tumor lesions are used in the RECIST criteria. Note: Lesions are either measurable or non-measurable using the criteria provided below.

8.3.1 Measurable disease

Measurable lesions are defined as those that can be accurately measured in at least one dimension (longest diameter to be recorded) as >20 mm with conventional techniques (CT, MRI, x-ray) or as >10 mm with spiral CT scan. All tumor measurements must be recorded in millimeters (or decimal fractions of centimeters).

8.3.2 Non-measurable disease

All other lesions (or sites of disease), including small lesions (longest diameter <20 mm with conventional techniques or <10 mm using spiral CT scan), are considered non-measurable disease. Bone lesions, leptomeningeal disease, ascites, pleural/pericardial effusions, lymphangitis cutis/pulmonis, inflammatory breast disease, abdominal masses (not followed by CT or MRI), and cystic lesions are all non-measurable.

8.3.3 Target lesions

All measurable lesions up to a maximum of five lesions per organ and 10 lesions in total, representative of all involved organs, should be identified as **target lesions** and recorded and measured at baseline. Target lesions should be selected on the basis of their size (lesions with the longest diameter) and their suitability for accurate repeated measurements (either by imaging techniques or clinically). A sum of the longest diameter (LD) for all target lesions will be calculated and reported as the baseline sum LD. The baseline sum LD will be used as reference by which to characterize the objective tumor response.

8.3.4 Non-target lesions

All other lesions (or sites of disease) should be identified as **non-target lesions** and should also be recorded at baseline. Non-target lesions include measurable lesions that exceed the maximum numbers per organ or total of all involved organs as well as non-measurable lesions. Measurements of these lesions are not required, but the presence or absence of each should be noted throughout follow-up.

8.3.5 Guidelines for Evaluation of Measurable Disease

All measurements should be taken and recorded in metric notation using a ruler or calipers. All baseline evaluations should be performed as closely as possible to the beginning of treatment and never more than 4 weeks before the beginning of the treatment.

The same method of assessment and the same technique should be used to characterize each identified and reported lesion at baseline and during follow-up. Imaging-based evaluation is preferred to evaluation by clinical examination when both methods have been used to assess the antitumor effect of a treatment.

Clinical Lesions will only be considered measurable when they are superficial (e.g., skin nodules and palpable lymph nodes). In the case of skin lesions, documentation by color photography, including a ruler to estimate the size of the lesion, is recommended.

Chest x-ray Lesions on chest x-ray are acceptable as measurable lesions when they are clearly defined and surrounded by aerated lung. However, CT is preferable.

Conventional CT and MRI These techniques should be performed with cuts of 10 mm or less in slice thickness contiguously. Spiral CT should be performed using a 5 mm contiguous reconstruction algorithm. This applies to tumors of the chest, abdomen, and pelvis. Head and neck tumors and those of extremities usually require specific protocols.

Ultrasound (US) When the primary endpoint of the study is objective response evaluation, US should not be used to measure tumor lesions. It is, however, a possible alternative to clinical measurements of superficial palpable lymph nodes, subcutaneous lesions, and thyroid nodules. US might also be useful to confirm the complete disappearance of superficial lesions usually assessed by clinical examination.

Endoscopy, Laparoscopy The utilization of these techniques for objective tumor evaluation has not yet been fully and widely validated. Their uses in this specific context require sophisticated equipment and a high level of expertise that may only be available in some centers. Therefore, the utilization of such techniques for objective tumor response should be restricted to validation purposes in reference centers. However, such techniques may be useful to confirm complete pathological response when biopsies are obtained.

Histology These techniques can be used to differentiate between partial responses (PR) and complete responses (CR) in rare cases (e.g., residual lesions in tumor types, such as germ cell tumors, where known residual benign tumors can remain).

The cytological confirmation of the neoplastic origin of any effusion that appears or worsens during treatment when the measurable tumor has met criteria for response or stable disease is mandatory to differentiate between response or stable disease (an effusion may be a side effect of the treatment) and progressive disease.

8.3.6 Response Criteria

Evaluation of target lesions:

8.3.6.1 Complete Response (CR):

Disappearance of all target lesions

8.3.6.2 Partial Response (PR):

At least a 30% decrease in the sum of the longest diameter (LD) of target lesions, taking as reference the baseline sum LD

8.3.6.3 Progressive Disease (PD):

At least a 20% increase in the sum of the LD of target lesions, taking as reference the smallest sum LD recorded since the treatment started or the appearance of one or more new lesions

8.3.6.4 Stable Disease (SD):

Neither sufficient shrinkage to qualify for PR nor sufficient increase to qualify for PD, taking as reference the smallest sum LD since the treatment started

8.3.6.5 Clinical benefit rate (CBR):

Objective responses (complete or partial response [PR] as well as stable disease [SD] \geq 8 weeks)

8.3.6.6 Progression free survival (PFS):

Time from randomization until objective tumor progression or death from any cause

8.3.6.7 Overall survival (OS):

Time from randomization until death from any cause

8.3.6.8 Objective response rate:

Proportion of patients with tumor size reduction of a predefined amount and for a minimum time period

8.4 Safety

All subjects who receive at least one dose of study treatment will be valid for the safety analysis.

All observations pertinent to the safety of the study treatment will be recorded and included in the final report.

Safety variables include the following: AEs, laboratory changes (complete blood counts, electrolytes, chemistry, and coagulation), changes in vital signs (blood pressure, heart rate, respiratory rate, and temperature) and ECG and, in some instances, changes in chest x-ray images, as produced at the investigator's discretion (e.g., for evaluation for pneumonia).

All AEs whether considered drug-related or not, will be reported in with a diagnosis, start/stop dates, action taken, whether treatment was discontinued, any corrective measures taken, outcome, and other possible causes. For all events, the relationship to treatment and the intensity of the event will be determined by the investigator.

This trial will use the NCI-CTCAE v4.0 criteria for assessment of toxicity and SAE reporting with regard to toxicity grade.

8.4.1 Data safety Monitoring Plan:

The Georgetown Lombardi Comprehensive Cancer Center will be responsible for the data and safety monitoring of this multi-site trial. As this study is an investigator initiated exploratory study utilizing an FDA approved drug it is considered a moderate risk study which requires real-time monitoring by the PI and study team and semi-annual reviews by the LCCC Data and Safety Monitoring Committee (DSMC).

The Principal Investigator and the Co-Investigators will review the data including safety monitoring at their weekly institution based disease group meetings and on monthly teleconferences.

All Severe Adverse Events (SAEs) are required to be reported to the IRB. Based on SAEs, the IRB retains the authority to suspend further accrual pending more detailed reporting and/or modifications to further reduce risk and maximize the safety of participating patients.

Progress on the trial and the toxicities experienced will be reviewed by the LCCC Data and Safety Monitoring Committee every 6 months from the time the first patient is enrolled on the study. Results of the DSMC meetings will be forwarded to the IRB with recommendations regarding need for study closure.

DSMC recommendations should be based not only on results for the trial being monitored as well as on data available to the DSMC from other studies. It is the responsibility of the PI to ensure that the DSMC is kept apprised of non-confidential results from related studies that become available. It is the responsibility of the DSMC to determine the extent to which this information is relevant to its decisions related to the specific trial being monitored.

A written copy of the DSMC recommendations will be given to the trial PI and the IRB. If the DSMC recommends a study change for patient safety or efficacy reasons the trial PI must act to implement the change

as expeditiously as possible. In the unlikely event that the trial PI does not concur with the DSMC recommendations, then the LCCC Associate Director of Clinical Research must be informed of the reason for the disagreement. The trial PI, DSMC Chair, and the LCCC AD for Clinical Research will be responsible for reaching a mutually acceptable decision about the study and providing details of that decision to the IRB. Confidentiality must be preserved during these discussions. However, in some cases, relevant data may be shared with other selected trial investigators and staff to seek advice to assist in reaching a mutually acceptable decision.

If a recommendation is made to change a trial for reasons other than patient safety or efficacy the DSMC will provide an adequate rationale for its decision. If the DSMC recommends that the trial be closed for any reason, the recommendation will be reviewed by the Associate Director for Clinical Research at G-LCCC. Authority to close a trial for safety reasons lies with the IRB, with the above described input from DSMC and the AD for Clinical Research.

